2.2.2. Secondary Endpoints

- Change in FPG from Baseline to Week 26.
- Change in body weight from Baseline to Week 26.
- Incidence of HbA1c of <7% (53 mmol/mol) at Week 26.
- Change in systolic and diastolic blood pressure from Baseline to Week 26.
- Change in HbA1c, FPG, and body weight from Baseline to Weeks 52 and 104.
- Incidence of HbA1c <7% (53 mmol/mol) at Weeks 52 and 104.
- Incidence of HbA1c ≤6.5% (48 mmol/mol) at Weeks 26, 52 and 104.
- Change in systolic and diastolic blood pressure from Baseline to Weeks 52 and 104.
- Proportion of subjects requiring glycemic rescue therapy up to Weeks 26, 52 and 104.

- Time to glycemic rescue therapy up to Weeks 26, 52 and 104.
- Endpoints related to pharmacokinetics of ertugliflozin.

Secondary endpoints related to bone safety are:

- Change in BMD as measured by DXA at the lumbar spine (L₁-L₄), femoral neck, total hip and distal forearm from Baseline to Week 26.
- Change in BMD as measured by DXA at the lumbar spine (L₁-L₄), femoral neck, total hip and distal forearm from Baseline to Weeks 52 and 104.
- Change from baseline in bone biomarkers at Weeks 26, 52 and 104.

As part of a large Phase 3 program for ertugliflozin, this protocol will contribute safety data to a program-wide meta-analysis of clinical cardiovascular events. Additional detail is provided in [Section 7.8.1](#).

To maintain the ability of the trial to provide information on long-term safety data, subjects who discontinue investigational product and do not withdraw consent will thereafter be contacted via telephone by the Investigator/qualified designee according to the same schedule as if the subject were still taking investigational product (ie, according to [Section the Schedule of Activities](#) and [Section 6](#)). Such subjects will be asked to return to the clinic at the time of the Week 104 visit. Additional details are provided in [Section 6.7](#).

This trial will utilize an external Data Monitoring Committee (E-DMC) to periodically review safety data.

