
It is also designed to evaluate the longer-term efficacy, safety and tolerability of ertugliflozin during the entire 104-week treatment period, which includes a 78-week double-blind extension period. A key purpose of this 78-week double-blind, extension period is to collect additional safety data of ertugliflozin on BMD. The effect of ertugliflozin on BMD will be assessed by DXA. All DXA data throughout the trial will be forwarded to a Central Evaluation Facility to ensure standardization.

Approximately 600 subjects will be randomized to ensure that a minimum of 480 subjects (160 per arm) provide HbA1c data at the Week 26 primary timepoint. Given the plans not to replace those subjects who are withdrawn early, the 600 subjects randomized will control for the approximate 20% premature withdrawal rate for HbA1c data to allow for withdrawn subjects who will still be included in the analysis, but will not necessarily have Week 26 data available. However, a 15% premature withdrawal or non-evaluable rate has been assumed for the BMD data, as this will not be censored if glycemic rescue therapy is taken prior to Week 26. So, the post glycemic rescue therapy data from subjects who require rescue therapy prior to Week 26 will be censored from primary and secondary efficacy analyses. For the bone safety endpoints (BMD and bone biomarkers), all data will be included (including results after glycemic rescue initiation). After the Week 26 visit, Phase A data will be unblinded for limited staff from the Sponsor but not for the Investigator and the subject, or any study team members involved in the day-to-day running of the trial, including site and central monitoring staff.

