Procedures will be put in place and described in the Informed Consent Document to ensure that if a subject loses contact with the trial site, alternative measures will be utilized for the collection of information on clinical cardiovascular events. This may include contacting family members and health care providers and, when applicable, using subject location services. Sites should make at least three attempts for a telephone contact. If the three attempts of telephone contact are unsuccessful, sites should make at least two attempts to

090177e1848ce2dd\Approved\Approved On: 23-Sep-2013 15:48

reach the subject via certified letter. All attempts to contact a subject and information received during contact attempts must be documented in the subject's medical record. In any circumstance, every effort should be made to document subject outcome, if possible.

Subjects who are discontinued from investigational product but agree to continue to participate in the trial by providing follow-up information can have medical and diabetes management by their managing physician or Investigator, as appropriate. These subjects may initiate any other therapy as needed (previously prohibited medications may be used). After discontinuation of investigational product, Pfizer or its designee will continue to reimburse/supply (as specified in [Section 5.6.1](#)), glimepiride or insulin (for those rescued) until trial completion. The Investigator should ensure that the subject has enough open-label rescue medication until the next scheduled in clinic visit. Procurement of any other oral AHAs, is the responsibility of the subject.

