7.6. Dual-Energy X-Ray Absorptiometry (DXA)

7.6.1. Bone Mineral Densitometry

Bone densitometry will be performed in facilities qualified and approved by the Sponsor or its designee.

DXA scanning procedures will be standardized and all the scans will be monitored and centrally analyzed by a Central Evaluation Facility according to a specific protocol. Procedures to be followed by the bone densitometry facilities to maintain quality control will be provided in a separate manual. The hardware used should remain the same for the duration of the trial. Software upgrades to DXA equipment must be approved in advance by the Central Evaluation Facility.

BMD of lumbar spine (L₁-L₄), femoral neck, and total hip and distal forearm will be measured by DXA at all time-points as mentioned in the [Schedule of Activities](#). The left hip should be evaluated unless prevented by pathology, in which case the right hip will be evaluated throughout the trial.

Screening DXA scan should be performed at Screening Visit 3, or sometime between S3 and at least ten days before the Day 1 visit. These scans will be submitted to the Central

Evaluation Facility for assessment of eligibility. Assessment of eligibility will be returned to the site before Day 1 visit and results of the Screening DXA must be available prior to subject randomization.

Follow up DXA scans will be performed at Week 26, 52 and 104 visits and submitted to the Central Evaluation Facility for assessment. Follow-up scans should be obtained in a ± 14 day window from the scheduled Week 26, 52 visits and in a 14 day window prior to the Week 104 visit. Investigators will remain blinded to the results of these follow up scans, unless the subject meets criteria for rescue criteria as provided below.

In case of discontinuation of investigational product during Phase A, a DXA scan will be performed if the discontinuation occurs between Week 12 and Week 26. In case of discontinuation of investigational product during Phase B, a DXA scan will be performed if the discontinuation occurs at least 12 weeks from the previous scan.

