7.6.1.1. Rescue Criteria Related to Loss of BMD

Rescue criteria will be put into place for subjects who exhibit a significant reduction in BMD according to the protocol-defined criteria. Subjects with a reduction in BMD from baseline of $>7\%$ at any anatomical site together with a T-score <-2.5 at the Week 26 or Week 52 follow-up scans, will have a complete unscheduled DXA performed. If these values are confirmed based on a repeat, complete unscheduled DXA the Investigator or treating physician will be permitted to start any bone active therapy. In these cases, subjects should continue to receive ertugliflozin or matching placebo. The repeat, confirmatory DXA should be performed within 4 weeks from the initial reading.

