9.2.3. Analysis of Other Secondary Endpoints

9.2.3.1. Analysis of BMD

The changes in BMD from Baseline to Week 26 at the lumbar spine, femoral neck, total hip, and distal forearm will be key safety endpoints. A BMD analysis set will be defined to include all randomized subjects who have received at least one dose of investigational product and have at least one measurement of BMD at any time during Phase A of the trial including baseline and post-baseline time points. For analyses of changes in BMD, measurements obtained post glycemic rescue therapy will be utilized if available; however BMD measurements will be censored at the point of a subject taking BMD rescue therapy.

Changes from Baseline to Week 26 in BMD will be analyzed by fitting a constrained longitudinal data analysis model with terms for treatment, visit, treatment by-visit interaction and menopausal status randomization stratum. Least-squares means and 95% confidence intervals will be used to estimate the treatment effect (difference between ertugliflozin and placebo) at Week 26.

Analyses of BMD will also be conducted separately for the male and female subgroups and also for subjects who completed ≥ 20 weeks of study treatment. Another sub-group analysis will be conducted separately for women post-menopausal for ≥ 3 years after LMP

090177e1848ce2dd\Approved\Approved On: 23-Sep-2013 15:48

(approximately 50% of the overall study population). Descriptive statistics will also be provided for each of the four randomization strata.

Changes from baseline in other continuous endpoints (including bone biomarkers) will be summarized descriptively (including 95% confidence intervals for BMD endpoints) by treatment group (for all treatment arms in each phase) and time point. Categorical endpoints will be summarized using frequency tables for each treatment group and time point.

Bone biomarker data and PTH data will be censored from the analysis if the samples were collected >7 days from the last dose of investigational product. Data for these markers will also be censored for subjects who initiate rescue medication with any bone-active medication.

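### BMD is censored only at BMD rescue, so the Week 104 (and possibly Week 52) BMD summaries can include scans taken after other bone-active drugs or long after the last dose

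*Combined protocol and SAP*

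**What the plan says.** Section 9.2.3.1 uses BMD measurements after glycemic rescue if available; "however BMD measurements will be censored at the point of a subject taking BMD rescue therapy". Section 7.6.1.1 defines the trigger: a loss of more than 7% at any site together with a T-score below −2.5 at the Week 26 or Week 52 scan, confirmed by repeat DXA. At that point "the Investigator or treating physician will be permitted to start any bone active therapy", and ertugliflozin or placebo continues.

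Exclusion criterion 31 (Section 4.2) bars bisphosphonates, other drugs affecting bone turnover, and pioglitazone or rosiglitazone during the trial. Needing a prohibited drug is a reason to stop investigational product (Section 6.7.2, item 5). For subjects who have stopped but stay in follow-up, Section 6.7 states: "These subjects may initiate any other therapy as needed (previously prohibited medications may be used").

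On their later attendance, Section 2.2.2 says: "Such subjects will be asked to return to the clinic at the time of the Week 104 visit". Section 7.6.1 says: "Follow up DXA scans will be performed at Week 26, 52 and 104 visits", and the Week 104 procedures in Section 6.4.4 include DXA.

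Two further statements bear on which data count. Section 3: "For the bone safety endpoints (BMD and bone biomarkers), all data will be included (including results after glycemic rescue initiation"). Section 9.2.3.1, on the companion endpoints: "Bone biomarker data and PTH data will be censored from the analysis if the samples were collected >7 days from the last dose". Week 52 and Week 104 BMD are summarized descriptively, with 95% confidence intervals, by treatment group and time point.

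**The concern.** The plan treats bone-active drugs as confounders of BMD. Section 1.5 gives this as the reason for excluding their users, and BMD is censored at BMD rescue for the same evident reason. But the censoring rule is tied to one narrow protocol event. A subject who needs a bone drug for another reason, a fracture for example, stops investigational product, may then take the drug, and is asked back at Week 104. That drug is not BMD rescue as Section 7.6.1.1 describes it. A subject who stops for hyperglycemia and starts a thiazolidinedione is in the same position, and Section 9.1 itself cites that class as causing bone loss.

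Nor does BMD have a limit on time since last dose. Such scans would be reported under the randomized dose. This matters because Section 3 calls further BMD safety data a key purpose of the 78-week extension, and because BMD and biomarker summaries at the same visit could describe different subjects.

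**Working it through.** **1. The plan's own precision figure.** Inputs from Section 9.1: SD 3.3%, 200 per arm, 15% dropout at Week 26, 95% interval. Half-width = 1.96 × SD × √(2/n).
- Overall: n = 200 × 0.85 = 170; 1.96 × 3.3 × √(2/170) = 0.702%, against the stated ±0.7%.
- Post-menopausal ≥3 years (half the population): n = 100 × 0.85 = 85; 1.96 × 3.3 × √(2/85) = 0.992%, against about ±1.0%.

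Both reproduce. The point disputes no stated figure; the half-width only gives a scale.

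**2. Which scans the written rules admit.**

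| Situation | BMD | Bone biomarkers |
|---|---|---|
| Bone-active drug under BMD rescue | Censored (9.2.3.1) | Censored (9.2.3.1) |
| Bone-active drug taken after stopping, outside BMD rescue | No rule | Sample not taken or censored once >7 days off drug (7.7, 9.2.3.1) |
| Thiazolidinedione taken after stopping | No rule | As above |
| Long time off drug, no new drug | No rule | As above |

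The biomarker rule shows that off-drug visits were foreseen.

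**3. Whether off-drug subjects are scanned.** Sections 6.4.4 and 7.6.1 require a scan at discontinuation if it occurs between Week 12 and Week 26, or in Phase B at least 12 weeks after the previous scan. The later recall has no procedure list of its own. A recall DXA follows only because the recall is to the Week 104 visit, which includes DXA, and no off-drug exclusion is written. A subject stopping at Week 10 gets no discontinuation scan. If scanned on recall, that subject contributes a value 104 − 10 = 94 weeks after the last dose. Section 6.7 also allows subjects to stop drug and keep attending clinic, so off-drug Week 52 scans are possible.

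**4. Illustration of size (all inputs assumed).** The documents give no off-drug share, bone-drug use or drug effect.
- Dilution: let f be the off-drug share of an ertugliflozin arm's Week 104 scans, r the part of the effect kept off drug, and −1.0% the true on-drug difference. Observed = −1.0 × (1 − f) − 1.0 × f × r. With f = 5%, r = 0.5: −0.975%. With f = 30%, r = 0: −0.70%.
- Bone-active drugs: if a share g of an arm's subjects use a drug shifting BMD by b, that arm's mean change moves by g × b. The contrast between arms moves only by the difference in shares times b. For a difference of 2–10% and b from −2% to +4%, the extremes are 0.10 × (−2) = −0.2 and 0.10 × 4 = +0.4 points; the smallest shift, with b = ±2%, is 0.02 × 2 = 0.04.

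**The case against.** The strongest reply is that keeping every safety scan is a legitimate treatment-policy choice, and Section 3 says all bone data are included. That stands in part: it is a good reason not to make an on-treatment summary the sole main result. But the plan does not follow that policy consistently, since Section 9.2.3.1 censors BMD at BMD rescue and biomarkers more than 7 days off drug. The 7-day window need not suit BMD, but having no stated position is different from choosing a longer window.

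Second, a reader might infer that long-off-drug scans certainly enter the Week 104 result. The documents do not establish this. Discontinuers have their own DXA rule, done near the end of treatment, and the recall scan is inferred.

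Third, Week 52 and 104 BMD is descriptive. The modelled comparison, which Section 9.2.3.1 treats as key safety, is at Week 26 and has a separate analysis in subjects with at least 20 weeks of treatment. This stands, and it limits the consequence; the 20-week analysis does not, however, ensure that Week 104 scans are on drug.

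Fourth, BMD rescue therapy might be read broadly as any bisphosphonate start. That would still leave thiazolidinediones and off-drug time uncovered.

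Fifth, Section 5.5 already requires concomitant medication to be recorded, and Section 9 defers detail to a separate SAP whose text is not in the document. The SAP may close the gap. The off-drug contacts, though, are described (Section 6.7; Schedule of Activities, note d) only in terms of serious adverse events and clinical events.

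**Conclusion.** The gap is real and inexpensive to close. As written, no rule covers BMD scans taken after non-rescue bone-active drugs or long after the last dose, and the descriptive Week 104 summaries (possibly Week 52) can include them.

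The size cannot be derived from the documents. The illustrative shifts above lie within the ±0.7% Week 26 half-width, which is itself only a loose yardstick: the Week 52 and 104 objectives concern change from baseline in each ertugliflozin arm, and non-rescued placebo subjects are due to add glimepiride in Phase B.

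A reader might infer that the effect is to hide bone harm. The documents do not support a single direction. Off-drug dilution, or bone-building drugs in an ertugliflozin arm, would mask a loss; thiazolidinediones there would exaggerate it; equal use across arms would cancel in a contrast, though not in a within-arm change. Nor does anything show that stopping drug is the main source of bone-active confounding, or that BMD recovers off drug.

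The conclusion rests on reading the recall as including DXA and on the separate SAP not already covering the point.

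**What to change.** 1. In Section 9.2.3.1, extend BMD censoring from BMD rescue therapy to the start of any bone-active agent on the criterion 31 list, thiazolidinediones included, whether the subject is on or off investigational product.
2. For Weeks 52 and 104, report an on-treatment BMD summary, with a pre-stated maximum interval from last dose to scan, beside an all-scans summary. Make neither the sole main result. Give the number of excluded scans and the reasons, by arm.
3. State explicitly that recalled off-drug subjects have the Week 104 DXA.
4. Record bone-active and antihyperglycemic drugs at the off-drug contacts already scheduled; if starts are missed, no later analysis can identify the affected scans.

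Reconcile the all-data sentence in Section 3 with the result. None of this changes what treatment subjects may receive.

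The cost is analysis-plan wording, one extra BMD table and one medication question per contact. The statistical price is fewer scans in the censored and on-treatment summaries. The exclusion may also be informative: subjects treated after a fracture would drop out because of a bone outcome. That is why the all-scans summary must stay alongside.

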090177e1848ce2dd\Approved\Approved On: 23-Sep-2013 15:48

were observed following 12 weeks of dosing with ertugliflozin. There was a suggestion of changes in markers of bone resorption, though there did not appear to be a clear dose-dependent effect with increasing dose of ertugliflozin. In totality, the clinical relevance of these findings remains unclear. However, the effect of ertugliflozin on BMD will be evaluated in this trial, and all clinical fractures will be adjudicated throughout the Phase 3 program by an independent committee and will be included in a pooled analysis.

In the clinical program to date, no clinically significant changes from baseline in serum aminotransferases (ALT and AST) have been observed.

Phase 3 clinical trial data from another SGLT2 inhibitor, dapagliflozin, revealed a numerical imbalance in the rates of breast and bladder cancer in dapagliflozin-treated subjects compared to control.¹¹ The causal relationship to dapagliflozin for this finding is uncertain given the small number of events and the absence of any preclinical signal (ie, no reported increase in either tumor in carcinogenicity studies) with dapagliflozin. Moreover, in the larger clinical program of another SGLT2 inhibitor, canagliflozin, no cancer imbalance, including in breast or bladder cancer events, was reported. Because thorough evaluation of malignancies is important in the development program of all investigational medications, detailed information will be collected for subjects who develop a malignancy. This information could include but is not limited to relevant medical history, biopsy, or operative reports, etc.

Complete information for this compound may be found in the Single Reference Safety Document (SRSD), which for this study is the Investigators' Brochure for ertugliflozin (PF-04971729).

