1.5. Rationale for Study and Design

SGLT2 inhibitors lower blood glucose in an insulin-independent manner. Consequently, glucose lowering should be observed across the typical continuum of T2DM progression, ranging from subjects treated with diet and exercise alone to subjects receiving insulin.

This trial will assess the efficacy and safety of ertugliflozin added to the regimen of subjects who have inadequate glycemic control on metformin monotherapy at or near maximally effective doses (ie, ≥ 1500 mg per day). Subjects already on metformin monotherapy at protocol-specified doses (≥ 1500 mg per day) for at least 8 weeks at Screening Visit 1 and who meet other enrollment criteria, will go directly from Screening Visit 1 to Screening Visit 3 to enter the 2-week single-blind placebo run-in period.

In addition to subjects with inadequate control on metformin monotherapy at protocol-specified doses, a broader range of subjects will be screened for the study, including subjects on metformin in combination with another allowable single AHA agent, or metformin at a dose below the protocol-specified dose (ie, < 1500 mg per day). Other potentially eligible subjects, not yet on metformin monotherapy at protocol-specified doses, will be switched at Screening Visit 2 to a regimen of metformin monotherapy and need to attain a dose of ≥ 1500 mg per day and then enter a dose stable period, including at least 8 weeks on a stable dose of metformin monotherapy prior to Screening Visit 3, where they

will enter a 2 week single-blind placebo run-in period. These subjects will have HbA1c measured again at Screening Visit 3 to determine if they qualify for enrollment.

Beyond the effects of ertugliflozin mentioned above on electrolytes and bone biomarkers from Phase 2, a small decrease in BMD, of unclear significance, was observed in a clinical trial of one agent in the SGLT2 class (canagliflozin), but not in another (dapagliflozin). SGLT2-induced urinary caloric loss produces body weight loss, which may potentially reduce BMD.¹⁸ Based upon these observations, this trial will assess the effect of ertugliflozin on BMD, and also obtain data on the effect of ertugliflozin on bone biomarkers.

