16. **Objective:** To descriptively summarize pharmacokinetics of ertugliflozin in this study and provide PK data for potential population PK analysis.

Secondary objectives related to bone safety are:

17. **Objective:** At Week 26, to assess the effect on BMD as measured by DXA at the lumbar spine (L₁-L₄), femoral neck, total hip, and distal forearm for each of the two ertugliflozin arms ertugliflozin as compared with placebo.
18. **Objective:** At Week 26, to assess the effect on bone biomarkers of each of the two doses of ertugliflozin as compared with placebo.
19. **Objective:** At Week 52, to assess the change from baseline in BMD as measured by DXA at the lumbar spine (L₁-L₄), femoral neck, total hip and distal forearm for each of the two ertugliflozin arms.
20. **Objective:** At Week 52, to assess the change from baseline in bone biomarkers for each of the two ertugliflozin arms.
21. **Objective:** At Week 104, to assess the change from baseline in BMD as measured by DXA at the lumbar spine (L₁-L₄), femoral neck, total hip and distal forearm for each of the two ertugliflozin arms.
22. **Objective:** At Week 104, to assess the change from baseline in bone biomarkers for each of the two ertugliflozin arms.

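### Objective 18 asks for Week 26 bone biomarkers against placebo, but protocol Section 9.2.3.1 plans only by-arm summaries, with no dose-versus-placebo estimate or interval

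*Combined protocol and SAP*

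**What the plan says.** **Objectives (Section 2.1, repeated in the synopsis).** Objective 18 reads: "At Week 26, to assess the effect on bone biomarkers of each of the two doses of ertugliflozin as compared with placebo". Objective 17, for BMD at Week 26, uses the same comparator: "distal forearm for each of the two ertugliflozin arms ertugliflozin as compared with placebo". Neither has a hypothesis attached. Objectives 19 to 22, for Weeks 52 and 104, ask only for change from baseline in the ertugliflozin arms and name no comparator.

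**Analysis (Section 9.2.3.1).** BMD at Week 26 gets a constrained longitudinal (cLDA) model: "Least-squares means and 95% confidence intervals will be used to estimate the treatment effect (difference between ertugliflozin and placebo) at Week 26". The biomarkers fall under the sentence on the remaining continuous measures: "including bone biomarkers) will be summarized descriptively (including 95% confidence intervals for BMD endpoints) by treatment group (for all treatment arms in each phase".

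**Data handling.** Biomarker and PTH results are "censored from the analysis if the samples were collected >7 days from the last dose of investigational product", and are also censored once a bone-active rescue drug is started. Glycemic rescue does not remove them. Section 3 says: "For the bone safety endpoints (BMD and bone biomarkers), all data will be included (including results after glycemic rescue initiation".

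**Reason for collecting the markers.** Section 1.4 reports from Phase 2: "There was a suggestion of changes in markers of bone resorption". It adds that there was no clear dose dependence and that the clinical relevance is unclear. Section 1.5 then says: "this trial will assess the effect of ertugliflozin on BMD, and also obtain data on the effect of ertugliflozin on bone biomarkers".

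**Where the detail sits.** Section 9 leaves detailed methods to a SAP, which may modify the protocol's plans. That SAP was not available for this point.

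**The concern.** The objective asks for a comparison, and the stated analysis stops one step short of it. The wording of the objectives separates two cases: Week 26 bone objectives are framed against placebo, and later ones are not. By-arm description fits the later ones. For Week 26 biomarkers it leaves the reader to subtract one arm's summary from another's.

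At stake is pre-specification, not a decision rule. If the protocol names no contrast, then the scale (raw or log), the use of baseline and the set of subjects analysed remain open when Phase A is unblinded. The estimate and its uncertainty for a named secondary objective would then rest on choices made with the data in view, or on the reader's own unadjusted calculation.

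**Working it through.** **1. Objective against analysis, for the two Week 26 bone objectives**

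| | Objective 17 (BMD) | Objective 18 (biomarkers) |
|---|---|---|
| Comparator in objective | placebo | placebo |
| Hypothesis attached | none | none |
| Stated analysis, 9.2.3.1 | cLDA model | descriptive, by arm |
| Dose-minus-placebo estimate | yes | not stated |
| 95% CI for that estimate | yes | not stated |
| Analysis set | BMD analysis set | none defined |

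No other section fills the right-hand column. Section 9.2.2 gives cLDA models to FPG, body weight and the two blood pressures. Section 9.3 summarizes laboratory tests descriptively. The synopsis statistical methods give no biomarker contrast.

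**2. The plan's own precision figure, as a check on the formula**

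Inputs from Sections 5.1 and 9.1: about 600 subjects randomized 1:1:1, so 200 per arm; BMD SD 3.3%; 15% dropout; about half of subjects in the subgroup of women post-menopausal for 3 years or more.

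Half-width = 1.96 × SD × √(2/n), with n evaluable per arm.

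- Overall: n = 200 × 0.85 = 170; 1.96 × 3.3 × √(2/170) = 0.702%. The plan states 0.7%.
- Subgroup: n = 170/2 = 85; 1.96 × 3.3 × √(2/85) = 0.992%. The plan states about 1.0%.

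Both reproduce.

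**3. The same formula for the biomarkers**

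The documents give no SD for CTX or P1NP, so the result can only be in SD units. They give no evaluable rate either. The 20% HbA1c allowance does not carry over, because biomarker data are kept after glycemic rescue. The 15% BMD allowance does not carry over directly, because the 7-day rule is specific to the biomarkers and PTH. I therefore assume a range of 140 to 190 evaluable per arm (70% to 95% of 200).

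Half-width in SD units = 1.96 × √(2/n):

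| n per arm (assumed) | Half-width (SD) |
|---|---|
| 140 | 0.234 |
| 150 | 0.226 |
| 160 | 0.219 |
| 170 | 0.213 |
| 180 | 0.207 |
| 190 | 0.201 |

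These are unadjusted. They show that the estimate is feasible at the planned size. They do not measure a loss.

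**The case against.** The strongest reply has four parts.

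- **The SAP may already contain the contrast.** Section 9 is visibly not the whole plan: time to glycemic rescue is an endpoint, yet Section 9 states no method for it. This stands as a limit on scope. It does not remove the point, because for biomarkers the protocol is not silent: it states a specific analysis, and that analysis stops short of the objective.
- **Tiering by importance looks deliberate.** Section 9.2.3.1 calls Week 26 BMD a key safety endpoint and Section 9.1 gives it a precision calculation; biomarkers have neither. Objective 11 is also framed against placebo without a hypothesis, and its categorical parts go into frequency tables by arm. So the BMD parallel is not the protocol's only pattern. This stands, and it lowers the severity. Against it, Section 9.3 gives even Tier-2 adverse events a risk difference with a 95% CI for estimation only, so an interval without a hypothesis is within this protocol's own practice.
- **The comparison can be made from the summaries.** Placebo is randomized, concurrent and displayed. If mean, SD and n are reported, an unadjusted difference and interval follow. This largely stands. What is lost is the use of baseline and stratum, and a scale chosen in advance.
- **The Phase 2 link is weak.** A reader might infer that the missing interval is what would settle the Phase 2 resorption-marker signal. The documents do not say so: Section 1.4 answers that uncertainty with BMD evaluation and fracture adjudication, and Section 1.5 promises only to obtain biomarker data as well.

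**Conclusion.** The point holds for the protocol text. Objective 18 asks for each dose against placebo at Week 26, and Section 9.2.3.1 pre-specifies neither an estimate of that contrast nor its interval. It is a minor improvement: no test, alpha allocation or decision rule is affected, and the data are already collected at Day 1 and Week 26. The half-width of about 0.23 to 0.20 SD rests on the assumed 140 to 190 evaluable per arm and on an unadjusted comparison.

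Three stronger readings are not supported:

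- That a hypothesis test has been left out. Objective 18 has no hypothesis.
- That the trial will report no between-arm biomarker estimate. The SAP may add one.
- That the lack of a modelled between-arm bone comparison at Weeks 52 and 104 is a similar mismatch. Objectives 19 to 22 name no comparator, so the planned by-arm changes meet their wording. In Phase B the control arm may also be on blinded, open-label or no glimepiride (Sections 3 and 5.3.5.1), with possible rescue insulin (Section 5.6).

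**What to change.** Add to Section 9.2.3.1, or confirm in the SAP, before Phase A unblinding:

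> CTX and P1NP at Week 26 will be analysed with the cLDA model used for BMD, in all randomized, treated subjects with at least one measurement of that marker in Phase A, with the planned censoring. The analysis will be on the log scale (or another single scale fixed before Phase A unblinding). Each dose versus placebo will be reported as a ratio of geometric means (or as a difference if the untransformed scale is fixed) with its 95% CI, for estimation only and without multiplicity adjustment.

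Two details matter. The scale must be fixed in advance, because choosing it after looking for skewness is data-driven and changes the estimand from a difference to a ratio. The analysis set must be the marker's own, because the one defined in Section 9.2.3.1 requires a BMD measurement.

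The by-arm summaries stay as planned. The cost is a few sentences and a few extra tables, with no new data and no alpha. The downside is a set of intervals unadjusted for multiplicity, which should be labelled as such. If the sponsor intends description only, rewording Objective 18 to say so would also remove the mismatch, but would give the reader less.
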